4.3.3. Progression to Cirrhosis

The Sponsor will evaluate the viability of including progression to cirrhosis in the primary efficacy endpoint in a blinded fashion. The method of evaluating progression to cirrhosis will be described in a separate document.

5. ANALYSES TO EVALUATE THE FEASIBILITY OF CONTINUING THE STUDY

5.1. Study Discontinuation

Subject discontinuation, which will be tabulated by treatment group and overall, will include the number randomized, the number in ITT population for analysis, the number who withdrew from

investigational product and reason(s) for withdrawal, the number who started commercial use of OCA, the number who withdrew from study visits prior to completing the study and reason(s) for withdrawal, the number of subjects who were contacted for follow-up, the number who withdrew from the study, the number of subjects who withdrew from the study prior to a potential endpoint event, and the number of subjects who withdrew from the study prior to a positively adjudicated endpoint event. Subjects are considered to have withdrawn from the study if they discontinued study visits and did not consent to follow-up contact or medical record review or if they withdrew consent for follow-up contact or medical record review. Subjects are considered to have started commercial OCA if they discontinued treatment or study visits due to initiating commercial OCALIVA, or if OBETICHOLIC ACID is recorded as a concomitant medication. Percentages of the number treated in total within each category will be provided.

Subject discontinuation summaries by treatment group and overall will be repeated by baseline Child Pugh classification, baseline Rotterdam score, and by geography (region and country). Baseline Child Pugh classification and baseline Rotterdam scoring are described in [Section 7.4](#).

Subject discontinuation information will be used by the DMC, among with other factors, to assess feasibility of continued conduct of the study as designed.

5.2. Sample Size Recalculation

A sample size recalculation is included in order to re-assess the assumptions for the sample size and power evaluation. The original study sample size calculation assumed a 10-year study (4 years enrollment, 6 years follow-up) and 80% power to demonstrate a statistically significant difference between OCA and placebo on time to liver-related outcomes. The sample size recalculation described here allows for a 12-year study (10 years enrollment, 2 years follow-up) and 70% power to detect a difference between OCA and placebo on time to liver-related outcomes.

If the criteria for the DMC to recommend that the study stop for efficacy, ie, the estimated hazard ratio is less than δ^* , where δ^* is the hazard ratio efficacy criterion at the interim analysis, are not met at the interim analyses, the conditional power for rejecting the null hypothesis in favor of the alternative (ie, the probability of success at end of trial given the interim results) will be computed. If the conditional power is >70% at the interim analysis, the DMC will recommend that the study continue as is (ie, the study will not stop for efficacy nor will the sample size be increased). If the conditional power is less than 70% and the estimated hazard ratio is within the “promising zone” of δ^* and 0.85, the number of clinical endpoint events will be re-estimated using the methods described in [Cui, Hung and Wang 1999](#) to achieve a conditional power of at least 70% for the end-of-study primary endpoint analysis. If the re-computed required number of events is less than 127, the original required number of events, 127, will be used. The total number of subjects to be enrolled in the study will be recalculated based on the new number of required endpoint events, observed placebo hazard rate at data cut-off of the interim analysis, assuming a total study duration of 12 years allowing for 10 years accrual and 2 years of follow up. The placebo hazard estimate will be calculated by fitting an exponential survival curve to time-to-endpoint data from placebo subjects, limited to time prior to switching to commercial use of OCA. If the re-computed sample size is less than 428, the original sample size of 428 subjects will be used. If the conditional power is less than 70% and the hazard ratio is greater than 0.85, the DMC may request additional analyses to evaluate the

feasibility of continued conduct of the study as designed. Additional details on the sample size recalculation may be found in [Section 7.5](#).

6. DEVIATIONS FROM PROTOCOL

6.1. Number of Interim Analyses

Although the protocol did originally plan for two interim analyses, one at ~50% (64 events) and the other at ~75% (96 events) information fraction, the first interim analysis was postponed to occur after regulatory authority review of the interim SAP. As a result, it is anticipated that the first interim analysis will occur after the accrual of approximately 65% (83 events) of the required total clinical outcome events. The Sponsor proposed and the regulatory authority agreed that the second interim analysis be omitted. Regardless of the number of interim analyses, O’Brien-Fleming Boundaries will be used to determine the criteria for superiority. Table 2 provide the relevant estimates both for the original two-interim analyses and revised single-interim analysis scenarios.

Table 2: Stopping Criteria Based on O’Brien-Fleming Boundaries

Type 1 Error	Power	Information Fraction	Number of Clinical Events	Incremental α Spend	Cumulative α Spend	Reject for Efficacy if Hazard Ratio
Two Interim Analyses						
		50%	64	0.003	0.003	≤ 0.473
0.05	0.80	75%	96	0.018	0.019	≤ 0.611
		End of Study (100%)	127	0.044	0.050	≤ 0.695
Single Interim Analysis						
		65%	83	0.011	0.011	≤ 0.564
0.05	0.80	End of Study (100%)	127	0.047	0.050	≤ 0.697

6.2. Additional Sensitivity and Efficacy Analyses

As OCA is commercially available to many subjects enrolled in the study, informative censoring and its potential to induce bias in the primary efficacy analysis is a concern. To inform the DMC in its recommendation on the continued conduct of the study, the following additional sensitivity analyses will be conducted:

1. The hazard ratio will be estimated using Inverse Probability of Censoring Weighting (IPCW) techniques ([Robins 1999](#)). The DMC will use this analysis to assess the impact of censoring on the hazard ratio.
2. The primary efficacy analysis will be repeated using only data accrued prior to subjects discontinuing regularly scheduled study visits. The objective of this analysis is to assess whether the time subjects spend off-treatment/off study-visits is diluting the hazard ratio.

3. The primary efficacy analysis will be repeated using only data accrued prior to subjects starting commercial use of OCA. The objective of this analysis is to assess whether use of commercial use of OCA impacts the hazard ratio.

Additional efficacy analyses of correlation of time-to-event outcomes and biochemical response will be run as supportive information for primary endpoint evaluation and in support of FDA PMR 3057-3.

In addition, the Sponsor will evaluate the viability of including progression to cirrhosis in the primary efficacy endpoint in a blinded fashion (to be described in a separate document).

6.3. Study Discontinuation

To further inform the DMC on the potential existence of informative censoring, subject discontinuation information, which is already available for DMC review, will be further detailed by baseline disease severity. The DMC will consider observed differences in censoring rates by treatment group and baseline disease severity or lack thereof when making a recommendation regarding the feasibility to conduct of the study.

6.4. Sample Size Recalculation

Due to higher-than-expected study and treatment discontinuation rates and slower-than-expected enrollment rates, a sample size recalculation has been added in order to re-assess the assumptions for the sample size and power evaluation. The observed hazard ratio at data cut-off of the interim analysis will guide the assessment of the required number of events. Evaluation of the sample size needed to reach the required number of events will be based on the observed placebo hazard rate at data cut-off of the interim analysis, assuming a total study duration of 12 years allowing for 10 years accrual and 2 years of follow-up.

7. APPENDIX: GENERAL ANALYSIS RULES AND DATA CONVENTIONS

The general analysis rules and data conventions described herein that are pertinent to the interim analysis will be followed.

Individual subject data obtained from electronic case report forms (eCRFs), central laboratories, external sources, and any derived data will be presented in data listings by subject. All data listings that contain an evaluation date will contain a relative study day. Pre-treatment and on-treatment study days are numbered relative to the day of the first dose of investigational product which is designated as Day 1. The preceding day is Day -1, the day before that is Day -2, etc. The last day of investigational product is designated with an "L" (eg, Day 14L). Post-treatment study days are numbered relative to the last dose and are designated as Day 1P, Day 2P, etc.

All output will be incorporated into Microsoft Word rich text format (.rtf) files, sorted and labeled according to the ICH recommendations, and formatted to the appropriate page size(s).

Tabulations will be produced for appropriate demographic, Baseline, efficacy, and safety parameters.

For categorical variables, summary tabulations of the number and percentage of subjects within each category (with a category for missing data) of the parameter will be presented. Percentage calculations will be based on non-missing data, unless otherwise specified. Percentages are rounded to 1 decimal place, unless otherwise specified.

For continuous variables, the number of subjects, mean, standard deviation (SD), standard error of the mean (SEM), median, first and third quartiles (Q1 and Q3), minimum, and maximum values will be presented. Other summaries (eg, quartiles, 5%, 95% intervals) may be used as appropriate. The precision of summary statistics, unless otherwise specified, will be as follows: mean and median to 1 more decimal place than the raw data, and SD and SEM to 2 decimal places more than the raw data. In general, the decimal places should not exceed 3 decimal places unless appropriate. Confidence intervals (CIs) will be provided and will be rounded to 1 decimal place, unless otherwise specified, in the table and listing shell.

Time-to-event data will be summarized using Kaplan-Meier methodology using 25th, 50th (median), and 75th percentiles with associated 2-sided 95% CIs, as well as percentage of censored observations.

All statistical tests comparing groups will be conducted at the 2-sided, 0.05 level of significance, unless otherwise specified (eg, the primary efficacy analysis, [Section 4.2.1](#)). Summary statistics for each treatment group will be presented, as well as 95% CIs comparing groups.

7.1. Baseline Definitions

The Baseline value for statistical analyses of quantitative parameters is defined as the mean of all available study evaluations after the subject signs the informed consent and prior to the first administration of investigational product, unless otherwise specified. If there is only one evaluation prior to the first administration of investigational product then the available data from this evaluation will be used as the Baseline value.

Baseline values defined above will not change regardless if a subject stops taking investigational product and begins taking commercially marketed OCA.

7.2. Partial Dates

If only a partial date is available and is required for calculation, the following standards will be applied:

- Diagnostic Date (eg, PBC diagnostic date)
 - For missing day only – Day will be imputed as the first day of the month (ie, 1).
 - For missing day and month – Day and month will be imputed as the first day of the year (ie, 1 January).
- Start Dates (eg, event date, AE onset date, or start date of medication)
 - For missing start day only – Day will be imputed as the first day of the month (ie, 1) with the following exception: if the partial date falls in the same month and year as the date being used in the calculation (eg, first dose date, informed

consent date), then the partial date will be imputed to equal the date being used for the calculation.

- For missing start day and month – Day and month will be imputed as the first day of the year (ie, 1 January) with the following exception: if the partial date falls in the same year as the date being used in the calculation (eg, first dose date, informed consent date), then the partial date will be imputed to equal the date being used for the calculation.
- Imputed start dates must be prior to the stop date.
- Stop Dates (eg, AE resolution date or stop date of medication)
 - For missing stop day only – Day will be imputed as the last day of the month (ie, 28, 29, 30, or 31).
 - For missing stop day and month – Day and month will be imputed as the last day of the year (ie, 31 December).
 - Imputed stop dates must be on or after the start date.

All data recorded on the case report form will be included in data listings that will accompany the clinical study report.

7.3. Data Conventions

The precision of original measurements will be maintained in summaries, when possible.

Means, medians, SEMs, and SDs will be presented with an increased level of precision, where means and medians will be presented to one more decimal place than the raw data, and the SEMs and SDs will be presented to two more decimal places than the raw data. In general, the decimal places should not exceed three decimal places, unless appropriate.

For tables where rounding is required, rounding will be done to the nearest round-off unit. For example, when rounding to the nearest integer, values $\geq XX.5$ will be rounded up to $XX+1$ (eg, 97.5 will round up to 98), while values $<XX.5$ will be rounded down to XX (eg, 97.4 will round down to 97).

Percentages based on frequency counts will be based on available data, and denominators will generally exclude missing values, unless otherwise stated. For frequency counts of categorical variables, categories whose counts are zero will be displayed for the sake of completeness. For example, if none of the subjects discontinued due to “lost to follow-up,” this reason will be included in the table with a count of 0. Percentages based on frequency counts will be presented as a whole number (no decimal places), and values less than 1% will be presented as “<1%.” Values less than 100% but that round up from 99.5% to 100% will be presented as “>99%.”

Quantitative laboratory tests containing less than ($<$) and greater than ($>$) symbols are test results that are below and above quantifiable limits, respectively. In order to retain these values for analysis purpose, the following imputations will be done within the analysis datasets:

For laboratory test results that are below the quantifiable limit:

Imputed laboratory results = (numeric portion of the result) x 0.9.

For laboratory test results that are above the quantifiable limit:

Imputed laboratory results = (numeric portion of the result) x 1.1.

7.4. Standard Calculations

Variables requiring calculation will be derived using the following formulas:

- Time to event – The time to an event will be calculated in days as the date of the first occurrence of the event minus the date of first investigational product administration plus 1
- Days – A duration expressed in days between one date (*date1*) and another later date (*date2*) will be calculated using the following formulas:
duration in days = $date2 - date1 + 1$, where $date1 \geq \text{first dose date}$
duration in days = $date2 - date1$, where $date1 < \text{first dose date}$
- Months – A duration expressed in months is calculated as the number of days divided by 365.25/12 (approximately 30.4)
- Years – A duration expressed in years between one date (*date1*) and another date (*date2*) is calculated using the following formulas:
duration in years = $(date2 - date1 + 1)/365.25$, where $date1 \geq \text{first dose date}$
duration in years = $(date2 - date1)/365.25$, where $date1 < \text{first dose date}$
- Age – Age is calculated as the number of years from the date of birth (*DOB*) to the specified date, eg, date of informed consent (*DOIC*). If the month of *DOIC* < month of *DOB* or the month of *DOIC* = *DOB* and the day of *DOIC* < day of *DOB*, then the following formula is used:
age (years) = year of *DOIC* – year of *DOB* – 1.
Otherwise, the following formula is used:
age (years) = year of *DOIC* – year of *DOB*.
- Change from Baseline – Change from Baseline will be calculated as:
Change = post Baseline value – Baseline value
- Percentage change from Baseline – Change from Baseline will be calculated as:
Percentage change from Baseline = $([\text{post Baseline value} - \text{Baseline value}] / \text{Baseline value}) \times 100$
- MELD score is derived using the following formula:
 $MELD = 3.78 \times \ln[\text{serum bilirubin (mg/dL)}] + 11.2 \times \ln[\text{INR}] + 9.57 \times \ln[\text{serum creatinine (mg/dL)}] + 6.43 \times \text{aetiology}(0: \text{cholestatic or alcoholic}, 1: \text{otherwise}).$
- Child Pugh classification (Noncirrhotic/A/B/C) is defined as follows: Subjects deemed noncirrhotic at baseline by the PI are captured as “noncirrhotic” regardless of baseline Child-Pugh score and those without a cirrhosis assessment or who were

deemed cirrhotic at baseline are summarized by their baseline (Screening or Day 0) Child-Pugh category.

- Rotterdam Criteria (Mild/Moderate/Severe) is defined as follows:

Mild - Total Bilirubin \leq ULN and Albumin \geq LLN

Moderate - Total Bilirubin $>$ ULN and Albumin \geq LLN or

Total Bilirubin \leq ULN and Albumin $<$ LLN

Severe – Total Bilirubin $>$ ULN and Albumin $<$ LLN, where baseline values of total bilirubin and albumin are taken to be the average of all pre-dose measurements.

7.5. Sample Size Recalculation

With a single interim analysis at 65% information fraction, the interim analysis and final study analysis are anticipated to occur at 83 and 127 events, respectively. The pre-specified weights that will be used for the sample size re-assessment will be:

$$w_1 = \frac{D_1}{127}; w_2 = \frac{127 - D_1}{127}$$

D_I is the number of actual observed events at the interim analysis.

Let

- $\delta = \ln(HR)$
- b_1 and b_2 denote the α -level stopping boundaries at the planned interim and final analysis, respectively
- r denote the proportion of subjects in the OCA treatment group
- $Z_{j,cum}^*$ denote the Z-score based on the stratified logrank statistic at look j
- D_1^* and D_2^* denote the altered cumulative events at the interim and final analyses resulting from an adaptation of the original design
- $\hat{\delta}_j$ and $\widehat{se}(\hat{\delta}_j)$ denote the estimates of treatment effect and standard error of treatment effect from fitting the Cox proportional hazard model to the cumulative data at look j

The CHW statistic for the interim ($j = 1$) and final ($j = 2$) analyses are:

$$Z_{1,CHW}^* = \frac{\sqrt{w_1}Z^{*(1)}}{\sqrt{w_1}} \text{ and } Z_{2,CHW}^* = \frac{\sqrt{w_1}Z^{*(1)} + \sqrt{w_2}Z^{*(2)}}{\sqrt{w_1 + w_2}}, \text{ respectively,}$$

where $Z^{*(j)}$ is the incremental statistic at look j :

$$Z^{*(j)} = \frac{\sqrt{I_j^* Z_{j,cum}^*} - \sqrt{I_{j-1}^* Z_{j-1,cum}^*}}{\sqrt{I_j^* - I_{j-1}^*}}$$

and $I_j^* \approx \frac{1}{(\widehat{se}(\widehat{\delta}_j))^2}$

If the CHW statistic at the interim analysis is $Z_{1,CHW}^* = z_1$ and D_2^* cumulative events are required at the final analysis, the conditional power at the interim analysis is:

$$CP_{\delta}(z_1) = 1 - \Phi \left\{ b_2 \sqrt{1 + \frac{D_1}{D_2 - D_1}} - z_1 \sqrt{\frac{D_1}{D_2 - D_1}} - \delta \sqrt{r(1-r)} \sqrt{D_2^* - D_1} \right\}$$

Where the log hazard ratio δ will be estimated using $\widehat{\delta}_1$, the estimate of treatment effect from fitting the Cox proportional hazard model to the cumulative data at the interim analysis.

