8.6. Multiple Comparisons/Multiplicity

An interim analysis was conducted after 80 events were observed. A group sequential design using the O'Brien-Fleming type alpha-spending function ([Lan 1983](#), [Reboussin 2000](#)) was used to control the overall two-sided 0.05 significance level that is at an information fraction of 0.63 of the total of 127 events, corresponding to an alpha spend of 0.009. The primary analysis will be conducted at 2-sided 0.041 significance level. No interim analysis will be performed based on the updated endpoints and methodology. The primary endpoint analysis for European Medicines Agency (EMA) filing will be conducted at 2-sided 0.041 significance level.

For the final analysis, the hypothesis testing of key secondary analyses will compare placebo and OCA (the key secondary endpoints are stated in [Section 8.2](#)), provided that the primary efficacy endpoint comparison is statistically significant in favor of OCA. If the primary comparison is not statistically significant then comparison of the key secondary endpoints will be considered as supportive or supplemental. If the primary comparison is statistically significant, the key secondary endpoints will be tested hierarchically in the order described in [Section 8.2](#) at a 2-sided 0.041 significance level. All other secondary endpoints will be tested at nominal 0.041 alpha level.

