4. EFFICACY ANALYSES

4.1. Primary Efficacy Analysis and Multiplicity Adjustment

The primary efficacy endpoint will undergo one interim analysis prior to final database lock and results will be reviewed by the independent DMC. A group sequential design using the O’Brien-Fleming type alpha-spending function (Lan & DeMets 1983) (Reboussin 2000) will be used to control the overall two-sided 0.05 significance level allocated to hepatic clinical outcomes (Table 1). The interim analysis will occur after accrual of approximately 65% (83 adjudicated events) of clinical outcome events (actual number of events based on observed data at interim analysis will be used for analysis) and the final analysis will occur after the accrual of 127 adjudicated clinical outcome events. To determine the timing for conducting these analyses, the number of pre-adjudicated endpoint events will be monitored and used for the projection.

Stopping criteria for efficacy at the planned timepoints based on group sequential boundaries are provided in Table 1 for the Type I error rate comprising the sum of prespecified alpha for clinical outcomes and carried forward alpha from the interim analysis. The exact alpha level and corresponding hazard ratio criterion at the time of the interim analysis will be calculated based on the actual observed number of clinical events.

The criteria for the DMC to recommend that the study stop for efficacy will be met at the interim analysis when the estimated hazard ratio is less than δ^* , where δ^* is the hazard ratio efficacy criterion calculated based on observed data at the interim analysis.

Table 1: Stopping Criteria Based on O’Brien-Fleming Boundaries

Overall Type 1 Error	Overall Power	Information Fraction	Number of Clinical Events	Incremental α Spent	Cumulative α Spent	Reject for Efficacy if Hazard Ratio
0.05	0.80	65%	83	0.011	0.011	$\leq 0.564 (\leq \delta^*)$
		End of Study (100%)	127	0.047	0.050	≤ 0.697

Note: Estimates for information fraction and number of clinical events at interim analysis are provided in Table 1 for illustration, and the hazard ratio efficacy criteria δ^* will be calculated based on observed data.

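### The interim SAP's conditional-power formula carries the wrong sign on the log hazard ratio, so its 70% rule and event re-estimation do not work as printed

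*SAP*

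**What the plan says.** Section 7.5 of the interim SAP defines delta as ln(HR). It gives the conditional power at the interim as

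CP = 1 - Phi{ b2 sqrt(1 + D1/(D2 - D1)) - z1 sqrt(D1/(D2 - D1)) - delta sqrt(r(1 - r)) sqrt(D2* - D1) }.

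The closing sentence calls delta the log hazard ratio and estimates it by "the estimate of treatment effect from fitting the Cox proportional hazard model to the cumulative data at the interim analysis". The Z statistic is introduced only as something that will "denote the Z-score based on the stratified logrank statistic at look" j, with no statement of which sign favours OCA.

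Section 4.1 fixes the direction of the hazard ratio. The efficacy criterion "will be met at the interim analysis when the estimated hazard ratio is less than" the boundary value, and its Table 1 gives 0.564 at the interim and 0.697 at the end. HR is therefore OCA over placebo.

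Section 5.2 uses the conditional power twice. For the first decision: "If the conditional power is >70% at the interim analysis, the DMC will recommend that the study continue as is". If it is below 70% and the hazard ratio lies between the efficacy criterion and 0.85, events are re-estimated "to achieve a conditional power of at least 70% for the end-of-study primary endpoint analysis". If it is below 70% and the hazard ratio exceeds 0.85, the DMC may ask for further feasibility analyses.

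**The concern.** The structure 1 - Phi{b2... - z1... - effect...} is the probability of crossing an upper boundary. It is correct when z1, b2 and the effect term are all positive for benefit. With delta = ln(HR) the effect term is negative for benefit. Subtracting it raises the argument of Phi and lowers the conditional power. A better observed effect then projects a worse remainder of the trial, and planning more events makes the projection worse still.

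At stake is the interim decision on trial size: whether the study goes on unchanged, and how many events a re-estimation would ask for.

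**Working it through.** **Inputs.**
- D1 = 83 and D2 = 127 (Section 7.5: "the interim analysis and final study analysis are anticipated to occur at 83 and 127 events, respectively"). The current text of Section 7.5 does not define D2; I read it as the planned 127.
- r = 0.5, from the 1:1 randomisation (Section 2.1).
- b2 = 1.990, from the O'Brien-Fleming spending function named in Section 4.1 (two-sided 0.0466; Table 1 prints 0.047).
- Assumption: |z1| = |ln HR| sqrt(D1)/2, because the plan gives no interim Z.

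**The plan's own figures.** The document states no conditional power to reproduce, but the design around it does reproduce.
- Events for 80% power at HR 0.60, two-sided 5%, by Freedman's formula: (1.960 + 0.842)^2 x (1.6/0.4)^2 = 126, against 127 stated.
- O'Brien-Fleming spending at 83/127 gives an interim alpha of 0.0111 and b1 = 2.539. On Freedman's scale the HR is (9.110 - 2.539)/(9.110 + 2.539) = 0.564, as in Table 1.

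**Conditional power at HR 0.60, 127 events, Z and b2 positive for benefit.**
- Boundary term: 1.990 x sqrt(127/44) = 3.381.
- z1 = 0.5108 x 4.555 = 2.327, and 2.327 x sqrt(83/44) = 3.196.
- Effect term: delta x 0.5 x sqrt(44) = -0.5108 x 3.317 = -1.694.
- As printed: 1 - Phi(3.381 - 3.196 + 1.694) = 1 - Phi(1.879) = 3.0%.
- Sign corrected: 1 - Phi(3.381 - 3.196 - 1.694) = 1 - Phi(-1.509) = 93%.

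**Across observed hazard ratios, 127 events.**

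| Observed HR | Printed | Corrected |
|---|---|---|
| 0.564 | 4.5% | 98% |
| 0.60 | 3.0% | 93% |
| 0.65 | 1.7% | 77% |
| 0.70 | 1.0% | 51% |
| 0.75 | 0.6% | 27% |
| 0.85 | 0.2% | 3.4% |

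A simulation of the weighted (CHW) statistic, with the marginally different b2 = 1.986, agreed with the corrected column: 93.6%, 51.7% and 3.5% at HR 0.60, 0.70 and 0.85.

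**Where the branch changes.** The corrected value crosses 70% at HR of about 0.665. The printed value reaches 70% only at HR of about 0.26, where the trial would already have stopped. So for observed HR between about 0.564 and 0.665 the intended branch is to continue unchanged, and the printed formula sends the study to re-estimation instead. Above 0.665 both versions are below 70%, and the branch is the same.

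**Re-estimation.** At HR 0.70 the printed value is 1.0% with 127 events, 0.3% with 160 and 0.1% with 200. It falls as D2* grows, so no number of events from 127 upward gives 70%. With the sign corrected, 70% needs about 171 events at HR 0.70 and about 297 at HR 0.75.

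**Sensitivity.** The final SAP's Section 8.6 says "An interim analysis was conducted after 80 events were observed". With D1 = 80, HR 0.60 gives 2.1% printed and 93% corrected. With b2 = 2.034 (what HR 0.697 implies at 127 events: 0.361 x sqrt(127)/2) and D1 = 83, it gives 2.5% and 92%. The conclusion does not move.

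**Other sign conventions.** If Z and b2 are both negative for benefit, the formula returns one minus the conditional power: 6.6% at HR 0.60 and 96.6% at HR 0.85. If Z is negative for benefit and b2 positive, it is near zero for every HR below 1 and 69% at HR 1.5. Neither rescues the text, and the plan states neither.

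**The case against.** The best defence is that this is a slip of notation. Section 5.2 says in words that conditional power is the probability of success at the end of the trial given the interim results. A value of 3% at HR 0.60 that falls as events are added plainly contradicts that, and a programmer working from standard software would probably have the sign right. Re-estimation that returns no event number would also reveal itself. This is fair, but the formula is the only operational definition in the plan, and nothing in the text reverses the sign.

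A minus sign could have been lost when the PDF was read, since other symbols in Section 7.5 look damaged. That cannot be fully excluded. Against it, delta = ln(HR) stands in its own bullet and the closing sentence again calls delta the log hazard ratio.

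Reading HR as placebo over OCA would make the formula right, but the efficacy criterion in Section 4.1 rules that out.

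A reader might infer that the whole DMC rule cannot tell a promising result from a failing one. It still can in part: the 0.85 limit uses the hazard ratio directly and needs no conditional power. A reader might also infer that an ineffective drug would usually be told to continue unchanged. That needs Z and b2 both negative for benefit, a convention the plan does not state.

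Finally, the interim has been done and no other is planned. The final SAP does not use this formula, and it attributes early stopping to discontinuations, enrolment difficulties and site closure requests. This limits what a correction can change.

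**Conclusion.** The formula in interim SAP Section 7.5 is wrong under the document's own definitions. On the natural reading (Z and b2 positive for benefit), it gives 3.0% instead of 93% at HR 0.60 and at most about 4.5% for any trial that passes the interim without stopping for efficacy. The continue-unchanged branch is unreachable, the branch is wrong for observed HR of about 0.564 to 0.665, and the re-estimation to 70% cannot be solved.

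The error is confined to that sample-size decision. The efficacy boundary and the type I error do not depend on it. The figures rest on z1 approximated from the hazard ratio, D2 read as 127 and b2 = 1.990.

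A reader might go on to infer that the DMC was given a wrong number or took a wrong branch. The documents show no interim hazard ratio, conditional power or code, so they do not support that.

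**What to change.** In Section 7.5, define delta as -ln(HR) and its estimate as minus the Cox log hazard ratio. Alternatively, keep delta = ln(HR) and change the last term to + delta sqrt(r(1 - r)) sqrt(D2* - D1). Either way, state that Z and b2 are positive in favour of OCA, and define D2.

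Because the interim is over, issue this as an erratum. Have the independent statistician confirm from the archived interim output which sign was programmed, and recompute the conditional power if it was the printed one. Report in the CSR what was found and whether the Section 5.2 branch would have changed.

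The cost is one line of text and at most one recalculation from existing output, with no new data. The only downside is that the CSR may have to report that the DMC saw an incorrect value.
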